**Table 3 – Quantitative Data Collected and Timing\***

Data Item	Type	Source	Purpose	6-mo prior to trial	Baseline	End of 6 month trial
Age	Numeric	EHR & Survey	Demographic characterization; Risk for Bleeding: HAS-BLED		√	
Gender	Numeric code	EHR & Survey	Demographic characterization		√	
Race/Ethnicity	Numeric code	EHR & Survey	Demographic characterization		√	
Insurance status	Numeric code	EHR	Demographic characterization		√	
Zip Code	Numeric code	Survey	Demographic characterization		√	

Employment status	Numeric code	Survey	Demographic characterization		√	
Yearly income	Numeric code	Survey	Demographic characterization		√	
Education level	Numeric code	Survey	Demographic characterization		√	
Household occupants	Numeric code	Survey	Demographic characterization		√	
Self-reported ability to use a computer	Numeric code	Survey	Demographic characterization		√	√
Self-reported ability to use the internet	Numeric code	Survey	Demographic characterization		√	√
Current proxy MyChart access	Numeric code	Survey	Demographic characterization		√	√
Potential future MyChart proxy access	Numeric code	Survey	Demographic characterization		√	√
Self-reported MyChart usage	Numeric code	Survey	Demographic characterization		√	√
Current anticoagulation medication	Numeric code	EHR & Survey	Demographic characterization		√	√
Marital status	Numeric code	EHR	Demographic characterization		√	
Height	Numeric	EHR	Demographic characterization		√	
Weight	Numeric	EHR	Demographic characterization		√	
BMI	Numeric	EHR	Demographic characterization		√	
Date of AF diagnosis	Numeric	EHR	Demographic characterization		√	
Type of AF	Numeric code	EHR	Demographic characterization		√	
eGFR or Creatinine Clearance	Numeric	EHR	Risk for Bleeding: HAS-BLED		√	
History of Diabetes	Y/N	EHR	Risk of Stroke: CHA 2 DS 2 _VASc		√	
History of Coronary Artery Disease	Y/N	EHR	Risk of Stroke: CHA 2 DS 2 _VASc		√	
History of Congestive Heart Failure	Y/N	EHR	Risk of Stroke: CHA 2 DS 2 _VASc		√	
History of Hypertension	Y/N	EHR	Risk for Bleeding: HAS-BLED Risk of Stroke: CHA 2 DS 2 _VASc		√	
History of stroke/ TIA/thromboembolism	Y/N	EHR	Risk for Bleeding: HAS-BLED Risk of Stroke: CHA 2 DS 2 _VASc		√	
History of MI/ PAD/aortic plaque	Y/N	EHR	Risk of Stroke: CHA 2 DS 2 _VASc		√	
Bleeding History	Y/N	EHR	Risk for Bleeding: HAS-BLED		√	
Specific Medication	Y/N	EHR	Risk for Bleeding: HAS-BLED		√	
Alcohol Use	Y/N	EHR	Risk for Bleeding: HAS-BLED		√	
Arterial embolus	Y/N	EHR	Health outcome	6 mo. – Baseline		Baseline – 6 mo.

Hemorrhage	Y/N	EHR	Health outcome	6 mo. – Baseline		Baseline – 6 mo.
Hospitalizations	Y/N	EHR	Health outcome	6 mo. – Baseline		Baseline – 6 mo.
Stroke	Y/N	EHR	Health outcome	6 mo. – Baseline		Baseline – 6 mo.
Death	Y/N	EHR	Health outcome	n/a		Baseline – 6 mo.
Calls to Anticoagulation Treatment Unit (ATU)	Numeric	ATU	Burden/ Patient Engagement	6 mo. – Baseline		Baseline – 6 mo.
Prescription Refill Frequency	Numeric	EHR	Assess medication adherence	6 mo. – Baseline		Baseline – 6 mo.
Smart Pill Bottle Use	Numeric	Report	Daily report of pill bottle opening, date/time stamped		√	√
MAS	Numeric	Survey	Assess medication adherence		√	√
PAM	Numeric	Survey	Assess patient engagement		√	√
SUS	Numeric	Survey	Computer use self-efficacy		√	√
AF Knowledge Scale	Numeric	Survey	Assesses knowledge of AF disease		√	√
New Vital Sign	Numeric	Survey	Assesses health literacy		√	√
ACE	Numeric	Survey	Assess patient engagement		√	√
TUPI	Numeric	Survey	Assess patient personality			√
PHR Login Frequency	Numeric	EHR	Assess engagement	6 mo. – Baseline		Baseline – 6 mo.
PHR webpage and video view frequency	Numeric	EHR	Assess engagement			Baseline – 6 mo.
PHR messages/phone calls to study staff	Numeric/Qualitative	EHR	Burden/ Patient Engagement			Baseline – 6 mo.
Appointments scheduled	Numeric	EHR	Assess engagement			Baseline – 6 mo.

\*See Appendix for scoring of HAS-BLED risk for bleeding and CHA2DS2\_VASc risk of stroke

d) Qualitative Data Collection and Analysis:

We will conduct semi-structured interviews at the conclusion of the 6-month study period with all participants in both the control and experimental groups. This data will act to fill the gaps that remain in survey data, as it allows for a deeper examination of particular issues with people living with AF. Participants will be asked questions in order to flesh out more detail around the usage patterns of the tested technologies, patient engagement, technology acceptance and experience with patient-provider communication.

All interviews will be audio recorded, with participant permission and researchers will take field notes. Investigators will review the transcribed digital recordings and field notes and perform thematic analysis to develop

a codebook. All documents will be imported into NVivo, and identified by session date and time. The investigators will independently review each session's recording to identify patterns within the participants' responses, annotating the recording with relevant concepts through NVivo. Using the method of grounded theory and constant comparison, the investigators will meet in a series of three or more review sessions to compare concepts, resolve discrepancies in interpretation, explore the various meanings of words, discuss emergent themes, and resolve ambiguities, until consensus is achieved and potential biases in interpretation are reconciled. Important user themes will be built using this iterative process of reviewing and grouping concepts during the review sessions. The relevance and importance of themes will be assessed using a rating schema of frequency, convergence and intensity. Frequency represents the number of times that the topic appears in the users' discussion, and is documented using NVivo's frequency reporting feature. Convergence, the relative occurrence of the topic, will be assessed as high, medium, or low. Intensity is defined as the emotion and importance of the topic to the user, and will be assessed using a scale of high, medium or low based on a subjective analysis of the digital recording for vocal tone, pace and volume. According to grounded theory, we will continue an iterative process of review and data collection until no new concepts are discovered and content saturation is reached. A summary of relevant themes will be compiled and used to further describe the impact of the intervention.

**Table 4 – Qualitative Data Collected and Purpose**

Data Item	Type	Source	Purpose
Lifestyle challenges with AF	Narrative	Patient Interviews	Define needs for intervention Cover gaps in quantitative survey data related to health literacy
Barriers to medication adherence	Narrative	Patient Interviews	Define needs for intervention Cover gaps in quantitative survey data related to medication adherence
Concerns with anticoagulant use	Narrative	Patient Interviews	Define needs for intervention Cover gaps in quantitative survey data related to health literacy
Educational needs for AF	Narrative	Patient Interviews	Define needs for intervention Cover gaps in quantitative survey data related to health literacy
Experience with tested technologies	Narrative	Patient Interviews	Cover gaps in quantitative survey data related to Technology Acceptance

Barriers to use of tested technologies	Narrative	Patient Interviews	Cover gaps in quantitative survey data related to Technology Acceptance
Suggestions for change in tested technologies	Narrative	Patient Interviews	Cover gaps in quantitative survey data related to medication adherence
Usage patterns of patient portal	Narrative	Patient Interviews	Cover gaps in quantitative survey data - patient engagement
Experience with patient-provider communication	Narrative	Patient Interviews	Define needs for intervention Cover gaps in quantitative survey data - patient engagement

e) Intervention:

The study intervention was developed based upon findings from the first phase of the study. The intervention entails sending tailored health educational messaging through MyChart. In order to tailor the health education per patient, an algorithm was developed from the phase 1 findings to determine what messages each patient will receive based on their specific needs. The algorithm was created based on patients' length of AF diagnosis, length of time on current anticoagulant medication, type of anticoagulant medication, and history of past anticoagulant medication.

During enrollment, patients will be instructed to contact study staff if their anticoagulant medication is changed or permanently discontinued at any point during the study. If their anticoagulant medication is permanently discontinued, patients will be instructed to stay in the study even while they are not taking their anticoagulant. Sometimes patients' anticoagulation therapy is temporarily discontinued for surgery or other health reasons. In order to maximize patient safety when these temporary holds on medications occur, tailored messages related to medication administration and compliance will include a disclaimer that if their medication has been stopped then this information is supplementary and they should follow their doctor's instructions first and foremost.

Concurrent with the educational messages sent to patients through MyChart, patients will periodically be sent a short survey asking them to evaluate the health information they just received. These questions will enable patients to evaluate the content, timing and delivery format of the interventional messaging. The survey will be administered through Survey Monkey, and the MyChart message will contain a secure link to access the survey.

**ETHICAL CONCERNS**

## **CONSENT PROCESS AND DOCUMENTATION**

Informed consent will be obtained from patients before any study activities commence.

## **CONFIDENTIALITY PROTECTION**

Data collected through chart review will be coded with the key kept in a separate location. Any data stored electronically will be password protected, encrypted, stored on a secure server and will be kept in an office with limited access. Any paper files will be kept in an office with limited access.

## **SUBJECT WITHDRAWAL**

Patients may withdraw from the study at any time. If funding for this study should be stopped early patients will be notified by telephone. If a patient elects to withdraw, only data collected from enrollment to withdrawal date will be utilized.

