#### **Separate from standard of care:**

- Receive an AdhereTech smart pill bottle to use for dispensing their anticoagulation medication at home.
- Receive training on the use of the AdhereTech smart pill bottle and commit to using in their daily routine for their anticoagulant medication
- Receive one-on-one training aimed at use of the MyChart PHR
- Use the PHR intervention: patients in this group will have the MyChart intervention designed and built in Phase 1 of this study – tailored health messaging delivered via MyChart pertinent to non-valvular atrial fibrillation and oral anticoagulation and stroke.
  - In addition to the tailored health messaging, patients will also receive periodic messages asking them to evaluate the health information they have received.
- Participate in an initial study visit, which includes the enrollment and training process above, as well as one follow up study visit and exit interview at approximately 6 months.
- Complete a patient survey at the initial study visit and follow up visit at approximately 6 months
- Submit information about their prescription history related to their anticoagulant medication for the study period
  - Patients may obtain this information from their pharmacy or print it out from their online pharmacy account. Patients will receive a letter from the Principal Investigators and a Medication dispensing record form to provide to their Pharmacist requesting anticoagulant dispensing information required for the study. The printout will be collected by the patient or a study representative with permission from the patient.

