(ACE) Measure, a 12 question survey validated to measure patient engagement, and 7) Ten-Item Personality Inventory (TIPI), a ten question survey used to assess patient personality. The first six survey instruments will be incorporated into a baseline and follow-up patient survey to be built out in Survey Monkey®, an on-line tool to design, collect and analyze surveys and responses. The TIPI survey will be used only at the 6-month study follow-up visit. Survey Monkey enables covered entities to collect protected health information (PHI) in online surveys in a way that permits compliance with the Health Insurance Portability and Accountability Act of 1996 (HIPAA). SSL (Secure Sockets Layer), a protocol developed for transmitted private documents or information via the internet, creates a secure connection between a client and a server, encrypting sensitive information being transmitted through the web page. After consenting participants, we will ask them to complete demographic information and survey (Table 2).

Patient surveys will be comprised of questions aimed at assessing patient engagement, health literacy, and medication adherence. Patient engagement will be assessed using the validated survey instruments, the Patient Activation Measure (PAM) and the Altarum Consumer Engagement (ACE) Measure, number of logins to MyChart and secure messaging activity with provider/health coach. We will also evaluate health literacy using questions aimed at patient understanding of anticoagulant use in AF. Medication adherence will be measured using the MAS validated survey instrument developed by Morisky and patient pharmacy refill records. In an attempt to make the medication adherence data more robust, we will extract refill record data from electronic prescribing software (Surescripts) on study patients. In addition, all patients will use smart pill bottles to dispense their anticoagulation medication. These bottles will track medication adherence by the opening of the bottle cap, and will record data accordingly. The bottles will not be set up to alert patients or deliver any intervention for medication adherence.

In order to determine the exact tailored health messaging patients will receive, study staff will identify the following information in patients' electronic health records:

1. Duration of time since AF diagnosis (Approximate days, months, and/or years)
2. Current oral anticoagulant prescribed

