## **RISK ANALYSIS**

Potential risks (adverse effects) to subjects:

- Patients may feel uncomfortable answering questions on the survey(s) or interview(s).
- Possible risk of breach of confidentiality of personal and/or health information.
- Patients may feel anxious or stressed upon receiving push messaging through their PHR if they have difficulty understanding it.

Precautions taken to minimize risk:

Patients will be informed that they can decline to answer any questions at any time. All data will be stored in a password protected electronic format. Collection of Protected Health Information (PHI) will be limited to the amount necessary to achieve study aims. Data will be accessible to the study supporter (Janssen Scientific Affairs), Parkview Research Center study personnel as well as PRC's consultants, partners, and/or business associates who are directly involved in this study. Analog data will be stored in

designated areas with limited access. Computers/electronic files will be password protected. All data will be encrypted during electronic transmission.

Patients will be advised to contact the study doctor or the study coordinator to have their questions and concerns addressed regarding the condition-specific information provided through their PHR.

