### **SAEs and Special Reporting Situations**

All serious adverse events that have not resolved by the end of the study, or that have not resolved upon discontinuation of the subject's participation in the study, must be followed until any of the following occurs:

- The event resolves
- The event stabilizes
- The event returns to baseline, if a baseline value/status is available
- The event can be attributed to agents other than the study drug or to factors unrelated to study conduct
- It becomes unlikely that any additional information can be obtained (subject or health care practitioner refusal to provide additional information, lost to follow-up after demonstration of due diligence with follow-up efforts)

The Sponsor Investigator will transmit all SAEs and special situations following exposure to a Janssen product under study in a form provided by Janssen Scientific Affairs in accordance with the Transmission Methods noted below, in English **within 24-hours of becoming aware of the event(s).**

All follow-up information for serious adverse events that are not resolved at the end of the study or by the time of patient withdrawal must be reported directly by the Sponsor Investigator, **within 24 hours becoming aware,** to Janssen Scientific Affairs using Janssen Scientific Affairs' Serious Adverse Event Report

All available clinical information relevant to the evaluation of a related SAE or special situation is required.

- The Sponsor Investigator is responsible for ensuring that these cases are complete and if not, are promptly followed-up. A safety report is not considered complete until all clinical details needed to interpret the case are received. Reporting of follow-up information should follow the same timeline as initial reports.
- Copies of any and all relevant correspondences with regulatory authorities and ethics committees regarding any and all serious adverse events, irrespective of association with the Janssen Product under study, are to be provided to Janssen Scientific Affairs using a transmission method noted below **within 24 hours of such report or correspondence being sent to applicable health authorities.**

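### Cheap improvement: the withdrawal rule bars all later data and does not separate leaving study activities from refusing further use of records

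*Protocol*

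**What the plan says.** The Subject Withdrawal section lets patients leave at any time and gives one rule on their data: "If a patient elects to withdraw, only data collected from enrollment to withdrawal date will be utilized". It states no options or exceptions and cross-refers to no other section.

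The outcome sources that do not depend on the patient are set out in Phase 2:

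- Quantitative Data Collection and Analysis: "we will extract refill record data from electronic prescribing software (Surescripts) on study patients".
- Table 3: "Prescription Refill Frequency", hospitalization, stroke, hemorrhage, arterial embolus and death, all taken from the EHR and all covering baseline to month 6.

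Other places bear on partial participation:

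- The arm descriptions ask patients in both groups to "commit to using in their daily routine for their anticoagulant medication".
- Risk Analysis: "Patients will be informed that they can decline to answer any questions at any time".
- The Intervention section, on permanent discontinuation of the anticoagulant: "patients will be instructed to stay in the study even while they are not taking their anticoagulant".

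The appendix section on SAEs and Special Reporting Situations deals with leavers separately. Serious adverse events still open when a subject's participation ends fall under the wording "participation in the study, must be followed until any of the following occurs". On follow-up information about such events, the appendix has this wording: "not resolved at the end of the study or by the time of patient withdrawal must be reported directly by the Sponsor Investigator".

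**The concern.** A patient who is tired of the bottle, the messages or the surveys may have no objection to the study team continuing to read refill and hospital records. The protocol describes no step that finds this out. Once such a patient elects to withdraw, the rule stops use of every source at the same date, including sources that ask nothing of the patient.

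At stake are Aim 2 outcomes for the rest of the six months: refills from Surescripts and the EHR, and clinical events from the EHR. The trial is un-blinded and only one arm receives messages, so the loss could differ between arms, although nothing in the protocol shows that it will.

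The point belongs in the protocol. An analysis plan can decide how missing data are handled, but it cannot authorize use of data that the protocol bars.

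A smaller matter is that the rule says only data up to withdrawal will be used, while the appendix expects safety follow-up after withdrawal. The two sections do not refer to each other.

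**Working it through.** **1. The plan's own figures.** Inputs from the Phase 2 Sample Size paragraph: SD of MPR 10%, difference 5%, two-sided 5% level, 80% power, 64 completers per group, 20% dropout, 80 enrolled per group.

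- Normal approximation: n = 2 × (1.96 + 0.842)² × (10/5)² ≈ 62.8, so 63 per group. The two-sample t-test gives 63.8, so 64.
- Power of the t-test at 64 per group: 0.801.
- Enrollment: 64 / (1 − 0.20) = 80.

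The stated figures reproduce. Planned dropout is 80 − 64 = 16 per group, or 32 of 160.

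**2. How much record time falls after withdrawal.** The protocol does not give the number who elect to withdraw. Assume a share w of 160, leaving evenly over six months, so that each leaver has on average 3 months of records after leaving. The 20% row is a ceiling under the plan, because that figure covers all dropout and not only elected withdrawal.

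Total record time = 160 × 6 = 960 patient-months. Time after withdrawal = 160 × w × 3. Recoverable time = that figure × a, with a = 0.5 to 1.0 assumed for patient agreement and complete records.

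| w (assumed) | Patients | Patient-months after withdrawal | Recoverable | Share of 960 |
|---|---|---|---|---|
| 5% | 8 | 24 | 12–24 | 1.25–2.5% |
| 10% | 16 | 48 | 24–48 | 2.5–5% |
| 20% (ceiling) | 32 | 96 | 48–96 | 5–10% |

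**3. Which sources could be recovered.**

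- *No patient action needed:* Surescripts refills, EHR refill frequency and EHR clinical events.
- *Patient action or permission needed:* bottle openings, surveys, exit interview and pharmacy printout.

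Recovery is therefore partial. It also rests on Surescripts, whose feasibility as an adherence measure is itself Aim 3.

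**4. The withdrawal rule beside the safety appendix.** The rule limits what is used. The appendix requires follow-up and reporting of serious adverse events, and its duty to transmit them to the supporter concerns exposure to the Janssen product, here rivaroxaban. The appendix names patient withdrawal explicitly and lets follow-up end when the subject refuses to give more information. If the rule's limit means the research analysis alone, the two sections fit together. The Subject Withdrawal section does not say that this is its meaning.

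**The case against.** The strongest reply is that the rule is coherent and protects consent: what was gathered stays and what comes later is left alone. A records-only option would then be a preference. It stands that this is not an error.

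Three further points on that side also stand:

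- **The consent pages were not available.** One might infer that leavers are never asked about their records. That cannot be known; the consent form may already ask.
- **The rule covers only patients who elect to withdraw.** One might infer that anyone who stops the bottle or ignores messages is cut off. The protocol does not call this withdrawal and removes no one for non-use. It keeps patients in after the anticoagulant is permanently stopped. Patients lost to follow-up are not covered by the rule either.
- **The powered measure may not be fully recovered.** The sample size rests on MPR. Surescripts is added to strengthen the pharmacy refill records, and the printout needs the patient or the patient's permission.

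One might also infer a contradiction with the safety appendix. Because the appendix addresses withdrawal and accepts a subject's refusal, what remains is a missing clarification.

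Two stronger numerical readings are tempting:

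- *Power.* If all 16 planned dropouts per group were retained with usable MPR, the t-test power would be 0.882 at 80 per group. This treats every dropout as an elected withdrawal with complete records, and the stated 80% is already met without it.
- *Bias.* In a completer comparison with no true effect, the shift is the leavers' MPR deficit × the difference in dropout. With 15% against 25% dropout and a 5-point deficit it is 5 × 0.10 = 0.5 points; with 10% against 30% and a 20-point deficit it is 20 × 0.20 = 4.0 points; with equal dropout it is 0. The unequal rates, the deficits and the completer analysis are all assumptions from outside the protocol, so no bias is demonstrated.

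The reply does not remove the central point: for a patient who does elect to withdraw, the protocol bars record data that the patient might willingly allow.

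**Conclusion.** The point holds as a cheap improvement. For patients who elect to withdraw but would allow record use, the rule discards Surescripts and EHR outcome data up to month 6 without need.

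The number affected is unknown and, under the plan, at most the 20% total dropout (32 of 160). On the assumed inputs (5% to 20% withdrawing evenly over time, 50% to 100% recoverable), 1.25% to 10% of all patient-months of records could be kept. The arithmetic is simple, but withdrawal rate, timing and recovery are all assumptions. Patient-months describe the volume of data and are not the unit of any stated analysis. No effect on the MPR comparison is estimated, because the protocol does not say how leavers enter it.

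The documents support neither a power shortfall nor a demonstrated bias. The relation to the safety appendix needs one clarifying sentence and is not a shown conflict.

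**What to change.** Amend the Subject Withdrawal section, and the consent wording if it does not already contain the choice:

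1. Ask a patient who wants to leave whether Surescripts and EHR outcomes may still be collected and used to month 6.
2. If the patient agrees, use them. If not, stop at that date and use the data up to it.
3. Record the type and date of withdrawal.
4. Add one sentence saying whether the limit on use concerns the research analysis only, so that it reads consistently with the follow-up of serious adverse events in the appendix.

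If the consent form already offers a records-only choice, align the protocol section with it.

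The cost is two or three sentences, one consent choice and a minor IRB amendment, with no new visits or patients. Patients already enrolled would have to be asked. Recovery will be incomplete: it depends on patient agreement and on how complete the records are, and the pharmacy printout may still be missing.
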